7.5 Packaging and Labelling

ENMD-2076 will be packaged and labelled by AAI Pharma Services (Wilmington, NC) and stored by Fisher Clinical Services (Allentown, PA). Each bottle of bulk study drug will contain a label with the following information:

- ∞ ENMD-2076 50 mg
- ∞ CASI Pharmaceuticals Lot Number (example): 4392-001
- ∞ Contents: Number of capsules (100 capsules)
- ∞ Instructions: Take orally as directed
- ∞ Store at Ambient Temperature (15-25°C)
- ∞ Caution: New Drug – Limited by Federal Law to Investigational Use
- ∞ Sponsor: CASI Pharmaceuticals, Inc., Rockville MD, USA

7.6 Conditions for Storage and Use

ENMD-2076 will be stored under secure (with limited access), humidity-, and temperature-controlled conditions for the duration of the study until the material is returned to CASI Pharmaceuticals or destroyed by authorization from CASI Pharmaceuticals. The Study Monitor will inspect the drug storage area and review the drug accountability procedures discussed with the Investigator and personnel authorized to handle and/or dispense study drug. ENMD-2076 bottles will be stored at ambient temperature (15-25°C) in an area accessible only to authorized staff. Patients will be asked to store their one-month supply of drug at ambient temperature. Study drug inventory forms will be kept by the Investigator, or designee, and examined and reconciled by the Study Monitor throughout the study.

7.7 Method of Assigning Subjects to Treatment Groups

This is a non-randomized study with all eligible patients assigned to active treatment with ENMD-2076.

7.8 Dispensing and Accountability

Study medication should only be dispensed once a patient has (1) signed an informed consent form, (2) met all eligibility criteria for entry into the study, (3) completed all screening and continuing eligibility requirements, and (4) been assigned a patient identification number.

Only patients enrolled in the study may receive study medication. Only authorized study personnel (the Investigator and his/her designees) may administer study medication, in accordance with all applicable regulatory requirements.

The investigator is responsible for maintaining accountability for the receipt, dispensing, and return of all study medication.

7.9 Patient Compliance

Authorized site personnel will administer the Day 1 dose of ENMD-2076. A one-month (+7 days) supply of study drug will be dispensed to each patient following the Day 1 study visit of each cycle. Patients will be instructed to return all empty study medication containers, any partially used or unused study medication, and daily diary pages at each visit to ensure compliance and record study drug accountability. If a patient realizes they miss a dose within 4

hours of the scheduled time, the dose should be taken. Otherwise, they should delay until the next day and consider the dose missed. Doses should not be repeated for any vomited doses. Any missed or vomited doses should be noted in their dosing diary.

Information regarding study medication administration and compliance will be recorded in the CRF.

A patient may refuse to take study drug or withdraw consent from further participation in the study at any time. Study site personnel will establish patient compliance with the study procedures and dosing at each visit.

7.10 Prior and Concomitant Therapy

All prescription and non prescription concomitant medications should be recorded on the appropriate page of the electronic case report form (eCRF).

The in vitro studies implicate the involvement of cytochrome P450 enzymes CYP3A4 in the pathways involved in the metabolism of ENMD-2076. No formal drug-drug interaction studies have been completed with ENMD-2076 and drugs that are substrates, inhibitors, or inducers of cytochrome P450 CYP3A4. Patients who require agents on the provided list in [Appendix D](#) will be excluded from enrolling in the study. Patients who require such an agent during participation in the study may be allowed to continue if the following apply: they have stable or responding disease (as confirmed by the Investigator); no alternative treatment is available; and they have close clinical monitoring while they are enrolled in the clinical trial.

Grapefruit juice is also a well-known inhibitor of CYP3A4 and should not be consumed during participation in the trial.

Concomitant treatment, in therapeutic doses, with anticoagulants such as warfarin or warfarin-related agents, heparin, thrombin or Factor Xa inhibitors, or antiplatelet agents (eg, clopidogrel) are not allowed. Low dose aspirin (\leq 81 mg/day), low-dose warfarin (\leq 1 mg/day), and prophylactic low molecular weight heparin (LMWH) are permitted.

Radioembolization is not allowed but will allow palliative radiation.

Any other medication which is considered necessary for the patient's welfare, and which is not expected to interfere with the evaluation of the study drug, may be given at the discretion of the Investigator.

No other investigational agents are permitted during the entire duration of treatment with study drug.

8. EFFICACY AND SAFETY ASSESSMENTS

8.1 Primary Efficacy Variable(s)

Overall response rate using RECIST v 1.1 criteria. Response will be measured every two months after first study drug administration. Patients who went off therapy without evidence of disease progression will have CT scans every two months until progression.

8.2 Secondary Efficacy Variables

- ∞ 6-month progression free survival (PSF6) rate
- ∞ The median PFS and TTP as based on RECIST 1.1 and measured by time from first study drug administration until progression or death.
- ∞ The median Overall survival as measured by time from first study drug administration to death or study completion.
- ∞ Safety data will be collected from time of informed consent through study completion /withdrawal up to 30 days after the last dose of study medication by each subject.

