Tumor measurements will occur every two months (\pm 1 week) after initial study drug administration. The overall response rate will be determined based on RECIST v 1.1 criteria. Survival and time to progression will be determined as the time from first study drug administration until death from any cause or documented progression. Patients who discontinue therapy for any reason other than progression will continue to receive imaging until progression or death.

An interim analysis will be conducted after 16 patients will have reached study endpoints of responses per RECIST 1.1 criteria after two cycles of treatment.. The purpose of the interim analysis is to determine whether it is futile to continue the study.

NUMBER OF SUBJECTS (PLANNED): 29

DIAGNOSIS AND MAIN CRITERIA FOR INCLUSION:

Eligible patients must fulfil the following inclusion criteria:

1. Histologically or cytologically confirmed advanced not amenable to curative resection fibrolamellar carcinoma (FLC).
 - a) This review will be conducted by a pathologist at the participating site to confirm the diagnosis. If there is a discrepancy, a review of a different archived specimen if available (heterogeneity is common) and/or identify a liver pathologist at another site who can provide independent review.
 - b) Archived specimens will be collected for subsequent immunohistochemistry, genomic analysis and possibly other research.
2. All forms of prior local therapy are allowed as long as patients have either a target lesion, which has not been treated with local therapy and/or the target lesion(s) within the field of the local-regional therapy that has shown an increase of $\geq 20\%$ in size. Local-regional therapy must be completed at least 4 weeks prior to the baseline CT scan.
3. Patients with prior systemic regimens are allowed. There is no limitation to the number of previous systemic regimens but must have recovered from any toxicity attributable to prior therapy.
4. Are at least 4 weeks from major surgery or systemic therapy and recovered.
5. At least one measurable lesion by RECIST 1.1.
6. Male or non-pregnant, non-breastfeeding female at least 18 years of age. Patients aged at 12~18 years may be recruited but only at the site principle investigator's request and subject to IRB approval.
7. Have clinically acceptable laboratory screening results within certain limits specified below:
 - ∞ AST and ALT ≤ 5 times upper limit of normal (ULN)
 - ∞ Total bilirubin $\leq 3.0 \times$ ULN

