9. Subjects with history of another primary cancer, with the exception of: a) curatively resected non-melanoma skin cancer; b) curatively treated cervical carcinoma in situ; or c) other primary solid tumor with no known active disease present in the opinion of the investigator will not affect patient outcome in the setting of current FLC diagnosis.

TEST PRODUCT(S), DOSE AND MODE OF ADMINISTRATION: ENMD-2076 is provided as hard gelatin capsules containing 50 mg of drug.

Patients will receive a daily oral dose (fasting) of ENMD-2076 of 150, 200 or 250 mg/day based on body surface area.

DURATION OF TREATMENT: Following the Screening and Baseline Period (Day -28 to 1) each treatment cycle will consist of a 4-week Treatment Period (Cycle 1 to Cycle 6+). Patients will be treated until disease progression, unacceptable toxicity or death.

DISCONTINUATION FROM TREATMENT:

The Investigator or the Sponsor may discontinue individual patients from the study at any time. Patients will be encouraged to complete the study; however, they may voluntarily withdraw at any time. The Investigator or designee will document the reason for discontinuation. Patients who went off therapy without evidence of disease progression will have CT scans every two months until disease progression or death.

A patient will be withdrawn from treatment for the following reasons:

- ∞ Significant adverse event
- ∞ Pregnancy
- ∞ Disease progression
- ∞ Consent withdrawn
- ∞ Noncompliance

PRIMARY EFFICACY ENDPOINT:

Overall response rate based on RECIST v 1.1 criteria will be used to evaluate response every two months after first study drug administration. Patients who go off therapy without evidence of disease progression will have CT scans every two months until progression.

SECONDARY EFFICACY ENDPOINTS:

- ∞ Progression-free survival rate at 6 months (PFS6).
- ∞ The median PFS or TTP as based on RECIST 1.1 and measured by time from first study drug administration

until progression or death.

- ∞ The median overall survival as measured by time from first study drug administration to death or study completion.
- ∞ Safety data will be collected from time of informed consent through study completion /withdrawal up to 30 days after the last dose of study medication by each subject.

SAFETY ENDPOINTS:

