5.2 Secondary Objectives

The secondary objectives are:

- ∞ To evaluate the 6-month progression free survival (PS6) rate using RECIST v 1.1 criteria when patients with FLC are treated with daily oral ENMD-2076.
- ∞ To evaluate the median Progression Free Survival (PFS), Time to Progression (TTP), and Overall Survival (OS).
- ∞ To determine the safety of ENMD-2076 as defined by the frequency and severity of adverse events when patients with FLC are treated with daily oral ENMD-2076.

- ∞ To explore biomarkers predictive of tumor response to ENMD-2076 in FLC patients

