5.3 Endpoints

Revised RECIST criteria (version 1.1) as defined in [Appendix C](#) will be used to evaluate response. Response will be evaluated after every two cycles of treatment. Complete response (CR), partial response (PR), stable disease (SD), and progressive disease (PD) will be defined as outlined in the revised RECIST criteria, [Appendix C](#) and [Section 6.3](#). SD is defined if the disease is stable on two measurements or longer, i.e. 4 treatment cycles or longer. Progression free survival (PFS) is defined as the time from the first day of treatment to the first observation of disease progression or death due to any cause or last follow-up. PFS will be censored for patients who are alive and free of progression at the time of last follow-up. Duration of overall response is measured from the time measurement criteria are first met for CR/PR (whichever is first recorded) until the first date that recurrent or progressive disease is objectively documented (taking as reference for progressive disease the smallest measurements recorded on study). Patients who are removed from the study for reasons other than documented PD will be followed at 2 month intervals until study endpoint.

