10.4 Efficacy Analysis

We have designed this study using a Simon's Optimal two-stage design to allow for an early interim analysis to determine potential futility and an overall final analysis with criteria established to allow for sufficient power and type 1 error rate to provide results to support a submission of the study as a pivotal trial.

For the primary endpoint, the overall response rate will be examined using the RECIST v 1.1 criteria. Patients will first be examined in one of 4 categories – CR, PR, SD, PD (Complete response, Partial Response, Stable Disease, or Progressive disease, respectively). Next, patients will be dichotomized as responders (CR/PR versus non-responders). The null hypothesis that the true response rate is 2% will be tested against a one-sided alternative that the true response rate is 15%. In the first stage, 16 patients will have reached study endpoints of response s per RECIST 1.1 criteria after two cycles of treatment. If there are zero responses in these 16 patients, the study will be stopped. Otherwise, 13 additional patients will be accrued for a total of 29. The null hypothesis will be rejected if 2 or more responses are observed in 29 patients. This design yields a type I error rate of 9.4% and power of 90% when the true response rate is 15%. The probability of early termination due to drug inefficacy is 72%.

After the primary efficacy analysis is performed, a one-sided 95% confidence interval will be calculated using the Clopper-Pearson exact method for the response rate. This will determine the

lower bound for the response rate. If 2 or more patients respond out of 29 then the lower bound will exceed 1.2% providing evidence that the drug is active (i.e. ruling out 0% response). For each of the secondary endpoints, exploratory analyses will be performed. Progression Free Survival rate at 6 months (PFS6) and three time-to-event measures will be calculated. Time to Progression, progression free survival and overall survival. A Kaplan-Meier survival plot will be calculated for each of these measures and median time to event (i.e. survival) will be calculated for each measure.

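### Section 8.2 and the synopsis give TTP the same end point as PFS, so TTP as written duplicates PFS although sections 5.2 and 10.4 plan two separate measures

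*Combined protocol and SAP*

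**What the plan says.** Six places in the combined protocol and SAP bear on this point.

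- **Section 8.2** gives both measures one end point: "The median PFS and TTP as based on RECIST 1.1 and measured by time from first study drug administration until progression or death".
- **Synopsis, secondary efficacy endpoints** has nearly the same clause, with the two measures joined by *or*: "The median PFS or TTP as based on RECIST 1.1 and measured by time from first study drug administration". The sentence then ends on progression or death, as in 8.2.
- **Synopsis, study design** has the only other wording on how TTP is measured: "Survival and time to progression will be determined as the time from first study drug administration until death from any cause or documented progression".
- **Section 5.3** defines PFS but not TTP: "Progression free survival (PFS) is defined as the time from the first day of treatment to the first observation of disease progression or death". Death from any cause counts. The censoring rule there names PFS only: "PFS will be censored for patients who are alive and free of progression at the time of last follow-up".
- **Section 5.2** lists median PFS, TTP and OS side by side as things to be evaluated.
- **Section 10.4** counts them separately: "three time-to-event measures will be calculated. Time to Progression, progression free survival and overall survival". Each is to have a Kaplan-Meier plot and a median. The same section sets the status of these analyses: "For each of the secondary endpoints, exploratory analyses will be performed".

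**The concern.** TTP normally differs from PFS in one respect: a death without progression is an event for PFS and not for TTP. Section 8.2 removes that difference. An analyst who follows it will report the same quantity twice, once labelled PFS and once labelled TTP. A reader who assumes the usual meaning will take the second as a progression-only result.

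An analyst who instead follows the synopsis design sentence, read so that survival ends at death and TTP at progression, could report a different TTP from the same data. The study is open-label, so a choice left until the analysis would be made with the outcomes in view.

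**Working it through.** **1. The plan's own figures.** The documents state no figure for TTP or PFS. The only design figures concern the response rate. From section 10.4: 16 patients in stage 1, stop at 0 responses, 29 in total, reject at 2 or more.

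- Early termination at a 2% response rate: 0.98^16 = 0.724 (stated 72%).
- Probability of rejecting = 1 − (1−p)^16 − 16·p·(1−p)^15·(1−p)^13.
- At p = 0.02: 1 − 0.7238 − 0.1818 = 0.094 (stated 9.4%).
- At p = 0.15: 1 − 0.0743 − 0.0253 = 0.900 (stated 90%).

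All three reproduce. No time-to-event quantity enters them, so the TTP definition cannot change them.

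**2. The definitions side by side.** Let P be the time to documented progression and D the time to death, both from first dose. The first day of treatment (5.3) and first study drug administration (8.2) are the same origin.

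| Place | PFS ends at | TTP ends at | Censoring stated |
|---|---|---|---|
| 5.3 | min(P, D) | not defined | PFS: alive and progression-free at last follow-up |
| 8.2 | min(P, D) | min(P, D) | none for PFS or TTP |
| Synopsis, secondary endpoints | min(P, D) | min(P, D) | none for PFS or TTP |
| Synopsis, study design | not named | P, or min(P, D), depending on the reading | none |
| 5.2 and 10.4 | listed as its own measure | listed as its own measure | none |

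Under 8.2, TTP and PFS have the same origin and the same events for every patient. The Kaplan-Meier curves and medians can then differ only if different censoring is applied, and no censoring rule for TTP is given. Section 10.4 plans three measures, and 8.2 leaves two distinct ones.

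**3. The synopsis design sentence.** With *respectively* read in, survival ends at death and TTP at P, which contradicts 8.2 and the synopsis endpoint list. Without it, either event ends both measures, and the duplication returns. The sentence therefore conflicts with 8.2 on one reading and repeats the problem on the other.

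**4. Size if TTP were progression-only.** Assume constant hazards λp for progression and λd for death without progression, with such deaths treated as independent censoring for TTP. Let d = λd/(λp + λd), the share of first events that are deaths.

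- Median PFS = ln 2/(λp + λd).
- Median TTP = ln 2/λp = ln 2/[(1−d)(λp + λd)].
- Ratio TTP/PFS = 1/(1−d).

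| d (assumed) | Calculation | Ratio of medians |
|---|---|---|
| 5% | 1/0.95 | 1.05 |
| 10% | 1/0.90 | 1.11 |
| 20% | 1/0.80 | 1.25 |
| 30% | 1/0.70 | 1.43 |

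The documents give no value of d, so the table shows a range and is not an estimate for this trial.

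**The case against.** The best defence is that 8.2 and the synopsis are compressed sentences, each meant to give a measure its customary end point: progression for TTP, progression or death for PFS. The *or* in the synopsis list even suggests that the two terms were used loosely as near-synonyms. PFS is properly defined in 5.3, and the secondary analyses are exploratory with no decision rule. The protocol also continues imaging after patients stop treatment, until progression or death, which should limit deaths without documented progression and keep d low.

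Much of this stands. The text does not prove which meaning was intended, the consequence is small, and nothing in the documents supports a large d. The defence does not remove the defect, because 8.2 states one end point for both measures while 10.4 counts them as two. If the terms are synonyms, 10.4 is wrong; if they are not, 8.2 is.

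Two stronger readings are tempting and should be resisted.

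- A reader might infer that the plan is silent on deaths in TTP. It is not: taken literally, 8.2 counts death as a TTP event. What is missing is a TTP rule that would distinguish it from PFS.
- A reader might infer that the choice between censoring and a competing-risk analysis is open under this plan. Section 10.4 plans Kaplan-Meier for every measure, and cumulative incidence would be a different estimand that the plan does not mention.

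**Conclusion.** The point holds as a minor defect of definition. The end point stated for TTP in 8.2 and the synopsis endpoint list is the PFS end point, so one of the three planned time-to-event measures adds nothing as written. The synopsis design sentence does not cure this.

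The size is zero difference in events if 8.2 is followed. If TTP ended at progression only, the ratio of medians would be 1.05 to 1.43 for d from 5% to 30%. That range rests on constant hazards, on deaths being independent of progression risk, and on values of d that are assumed.

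A reader might infer that the trial's main result is in doubt. The documents do not support that: the primary endpoint is the response rate, and its error rates, the 29 patients and the stage 1 stopping rule do not involve TTP.

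**What to change.** Use one definition in both synopsis places, in 8.2 and in 10.4: TTP is the time from first dose to first documented RECIST 1.1 progression. Under the Kaplan-Meier method already planned, censor every patient without documented progression at the last tumor assessment, whether the patient is alive or has died. Reword the synopsis design sentence so that it cannot be read two ways. Keep PFS as in 5.3 and present TTP beside it, not in its place.

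If no separate measure is wanted, delete TTP from the objectives, the endpoint lists and 10.4. That resolves the conflict equally well.

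Either change is wording only, with no added scans or patients, although section 3.4 may require it to go through as an amendment because it touches an assessment variable. The statistical cost of keeping TTP is that censoring deaths assumes they are unrelated to the risk of progression, which may not be true in advanced disease.

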8.2.1 Objective Tumor Responses/Benefit Assessments

Tumor responses in patients will be determined by the RECIST guidelines (version 1.1) defined in [Appendix C](#). In the absence of significant treatment-related toxicity or clinical evidence of progressive disease, patients will be allowed to continue on 4-week cycles of ENMD-2076. The frequency and timing of the assessment of tumor burden/clinical benefit are described in [Table 4](#). Unscheduled benefit assessments may be conducted when clinically indicated during the study.

∞

8.2.2 Guidelines for Evaluation of Measurable Disease and Response

Guidelines for evaluation of measurable disease and response are outlined in Section 4 of [Appendix C](#).

The same modality of assessment and the same technique should be used to characterize each identified and reported lesion at baseline and during follow-up. Imaging-based evaluation should always be done rather than clinical examination unless the lesion(s) being followed cannot be imaged but are assessable by clinical exam.

Details regarding method of assessment (i.e., CT scan) are outlined in Section 3.2.2 of [Appendix C](#).

